3 STUDY OBJECTIVES AND ENDPOINTS

3.1 Objectives

The overall objective of this study is to explore the clinical efficacy of daridorexant and to further evaluate its safety and tolerability in subjects with insomnia and comorbid nocturia.

Based on the mode of action of daridorexant and the knowledge acquired during its development, it is reasonable to identify the following objectives to be explored in this study:

Efficacy objectives

The primary objective of this study is to assess the efficacy of daridorexant on insomnia in subjects with insomnia and comorbid nocturia. The following variables will be evaluated:

- a) Quantitative measure of sTST by the SDQ.
- b) Overall rating of the insomnia severity by the ISI[©] with a recall period of 2 weeks.
- c) Other SDQ-derived variables: (i) quality of sleep VAS, (ii) depth of sleep VAS, (iii) daytime alertness VAS, (iv) daily ability to function VAS, and (v) number of awakenings.

The secondary objective is to assess the efficacy of daridorexant on nocturia. There is no data for daridorexant in subjects with insomnia and comorbid nocturia. The following variables will be evaluated:

a) Voiding diary derived assessments: (i) time to the first nocturnal void, (ii) each voiding volume (nighttime and daytime) including total volume, (iii) number of nocturnal voids.

4 September 2023, page 36/122

- b) Lower urinary tract symptoms sub-score using the ICIQ-MLUTS and -FLUTS for male and female subjects, respectively.
- c) Quality of life relative to nocturia assessed by ICIQ-NQoL.

Other objectives will focus on patient's overall assessment ratings of their condition and symptoms including:

- a) PGA-S and PGI-C for insomnia and for nocturia.
- b) Quality of life using the EQ-5D-3L.
- c) Overall assessment of subjective treatment satisfaction by NRS.
- d) Subject preference for treatment.

In addition to efficacy and safety this study the following exploratory efficacy endpoints will be studied a) the sensitivity of the IDSIQ to detect clinical changes in this study population, and b) the use of narratives to report subject's perception of treatment effect.

Safety objectives

The safety objectives will be to assess the safety and tolerability of daridorexant based on:

- a) AE reporting.
- b) Occurrence of suicidal ideation, suicidal behavior and/or self-injurious behavior with/without suicidal intent based on the C-SSRS[©].
- c) Morning sleepiness as determined by morning sleepiness VAS.

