9.4 Sample size

The assumptions for the sample size calculations were determined using data from studies ID-078A202 and ID-078A301 for the treatment groups daridorexant 50 mg and placebo.

Data of sTST changes from baseline and the corresponding SDs were derived based on simulations using sTST data at Baseline and at Month 1 from the ID-078A301 study for the age group ≥ 55 years. Subsets of 50 subjects were randomly selected from both the daridorexant 50 mg and placebo groups and compared via t-tests for independent samples, with means and SDs averaged across 1000 iterations. The simulations resulted in a mean difference of the change from baseline to Month 1 in sTST of 26 min for daridorexant 50 mg.

Correlations between daridorexant 50 mg and placebo for sTST data were derived based on the cross-over study ID-078A202 (for subjects aged ≥ 65 years). The Pearson correlation coefficient was estimated at 0.58. Combining all the information above resulted in an SD of the difference in the change of sTST from baseline to Month 1 of 44 min (based on the variance/covariance formula).

Based on a two-sided type I error of 0.05, an estimated within subject mean difference of the change from baseline to Month 1 in sTST between daridorexant 50 mg and placebo of 26 min and an associated SD of 44 min, a total sample size of 50 subjects, in this cross-over setting, provides at least 90% power, based on a two-sided paired t-test. A smaller within subject mean difference between daridorexant 50 mg and placebo of 20 min still results in power of at least 80%.

9.4.1 Power considerations for the endpoint change from baseline to Week 4 in number of nocturnal voids assessed using a voiding diary

Sample size calculations/considerations for the endpoint change from baseline to Week 4 in number of nocturnal voids assessed using a voiding diary were performed based on two-sided paired t-tests for different scenarios:

- 1. Assuming a within-subject mean difference between daridorexant 50 mg and placebo in the number of nocturnal voids of 0.30 (averaged across 3 consecutive nights) after 4 weeks of treatment, and assuming an SD of the within-subject difference of 0.7, leads to approximately 80% power, based on 50 subjects and a type I error of 0.05, using a two-sided paired t-test.

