## 2 STUDY DESIGN AND FLOW

This is a post-approval, multi-center, double-blind, randomized, placebo-controlled, 2-way cross-over study assessing daridorexant at a dosing regimen of 50 mg, once daily, vs placebo over a 4-week treatment period in adult subjects of 55 years and older with insomnia and comorbid nocturia.

[figure not shown]
Approximately 50 subjects will be randomized in a 1:1 ratio to one of two treatment sequences: daridorexant 50 mg / placebo or placebo / daridorexant 50 mg.

The study will be conducted at approximately 18 sites in the United States, Spain, and Germany.

The study design is shown in Figure 1.

Page 9/50

Figure 1 Study design for ID-078A401

- The voiding diary is completed on 3 consecutive days following V1, V2 and V6 and on the 3 days immediately preceding V4 and V8
- <--> Daily completion of sleep diary from V1 to V8

D = day; EOS = end-of-study; EOTP = end-of-treatment period; V = visit.

The study comprises the following 5 periods: the screening period, TP I, washout period, TP II, and the safety follow-up period.

The **screening period** starts with the signing of the informed consent form at Visit 1 and ends with Randomization at Visit 2 or with a screening failure. It lasts 14–21 days.

**TP I** starts with the administration of the first dose of study treatment and ends on the day after the last dose of study treatment (Day 29). The study subjects will be treated for 4 weeks.

The **washout period** starts after completion of the TP I and lasts 14–21 days. During the washout period the subjects will not be treated at all and will be followed up for safety (5–10 days).

**TP II** starts with the administration of the first dose of the 'other' study treatment and ends on the day after the last dose of study treatment (Day 29). The study subjects will be treated for another 4 weeks.

The **safety follow-up period** starts on the day after the last dose of study treatment in TP II and ends at the EOS visit (5–10 days after EOTP II).

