# **6.1.2** Overall testing strategy

The primary endpoint will be analyzed based on an MMRM. Some sensitivity analyses will also be performed for the primary endpoint. Those analyses are not part of the testing strategy.

Hypotheses are defined as follows:

- H0: Mean of the within-subject changes in sTST from baseline to Week 4 between daridorexant 50 mg and placebo = 0;
- H1: Mean of the within-subject changes in sTST from baseline to Week 4 between daridorexant 50 mg and placebo ≠ 0.

The null hypothesis will be tested at a 2-sided 0.05 significance level.

A preview of the main analyses is given in Table 3 using the estimand terminology [ICH 2019]. Estimands are defined by five attributes: treatment condition of interest, target population, endpoint, strategy for addressing intercurrent events (i.e., premature discontinuation of treatment), and population-level summary.

The primary estimand is based on the primary endpoint: the difference in means between the two treatments in the change from baseline to Week 4 in sTST, regardless of treatment discontinuation. For the primary estimand, the treatment condition is daridorexant 50 mg once daily for up to 4 weeks whereas the alternative condition is placebo once daily for the

<sup>a Baseline is the mean value based on the screening sleep diary for sTST, performed on the 7 days preceding

<sup>b Week 4 is the mean value based on the sleep diary entries for sTST performed on study days 23–29 for each period.

same period. The other four attributes are given in the table below. The primary estimand follows a 'treatment policy' strategy.

The secondary estimand is also based on the primary endpoint. Intercurrent events are defined as premature treatment discontinuations. Details are provided in Table 3. The secondary estimand follows a 'hypothetical' strategy.

Table 3 Estimands for the primary objective

Estimand	Target population	Endpoint	Strategy for addressing intercurrent events	Population-level summary
Primary estimand	Subjects with insomnia associated to nocturia	Change from baseline to Week 4 in sTST	Treatment policy strategy, i.e., endpoint data after premature treatment discontinuation are used.	Treatment effect expressed as difference of LS Mean changes from baseline to Week 4 (daridorexant minus placebo; from MMRM)

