#### 6.3.1.3 Number of awakenings

The number of awakenings is collected daily via a Sleep Diary Questionnaire.

The change from baseline to Week 1–Week 4 in number of awakenings will be summarized by treatment. Observed values will also be summarized by treatment.

Definitions of the weekly averages are the same as described in Section 6.3.1.2.

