# 6.3.2.3 Changes from baseline to Week 1 and Week 4 in the volume of the first nocturnal void

The first nocturnal voiding volume is defined as the volume of the first nocturnal void collected after bedtime and before waketime.

The first voiding volume per night will be averaged across voiding nights. The mean first voiding volume and corresponding change from baseline will be summarized descriptively by visit and treatment.

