#### 6.3.3.1.2 Analysis

The change from baseline to Week 4 for all sub-scores of ICIQ-MLUTS and ICIQ-FLUTS will be summarized by treatment and sex. Observed values will also be summarized.

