#### 6.3.3.2.2 *Analysis*

The change from baseline to Week 4 for the overall ICIQ-NQoL score will be summarized by treatment. Observed values will also be summarized.

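### Six of the eight nocturia endpoints, and the number of awakenings, get by-treatment summaries only, so the cross-over reports no paired SE or CI for them

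*SAP*

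**What the plan says.** Protocol 3.1 makes nocturia the secondary objective and lists its variables, among them "Quality of life relative to nocturia assessed by ICIQ-NQoL". Protocol Table 3 turns that objective into eight endpoints. Protocol 9.2.3 defines no secondary endpoints, and 9.2.4 leaves the analysis of everything beyond the primary endpoint to the SAP.

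The SAP plans the following:

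- ICIQ-NQoL (6.3.3.2.2): "The change from baseline to Week 4 for the overall ICIQ-NQoL score will be summarized by treatment".
- Lower urinary tract symptoms (6.3.3.1.2): the change to Week 4 "for all sub-scores of ICIQ-MLUTS and ICIQ-FLUTS will be summarized by treatment and sex".
- Volume of the first nocturnal void (6.3.2.3): "The mean first voiding volume and corresponding change from baseline will be summarized descriptively by visit and treatment".
- Total night and daytime volume (6.3.2.4.2) and number of daytime voids (6.3.2.5.2): descriptive.
- Number of awakenings, a primary-objective variable (6.3.1.3): the change "in number of awakenings will be summarized by treatment".

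SAP 8.1 defines the default summary of a continuous variable as number of values, mean, SD, median, quartiles and range.

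Other endpoints do get a within-subject comparison. The number of nocturnal voids has an MMRM with a treatment difference and 95% CI (6.3.2.5.2). Time to first nocturnal void has a two-sided matched-pairs sign test (6.3.2.2). ISI, the VAS scales and IDSIQ have an MMRM (6.3.1.1, 6.3.1.2.2, 6.3.3.5.2; listed as additions in 11.4). Treatment satisfaction has a paired t-test with 95% CI (6.3.3.6).

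**The concern.** Protocol 4.3 chooses a cross-over because each subject serves as their own control, which lowers variability and allows a smaller sample. That gain appears only when the two treatments are compared within subjects. A mean and SD for each treatment do not show it, because the SE of the difference depends on the within-subject correlation, which the tables do not report.

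Protocol 3.5 accepts that only sTST is adequately powered, yet expects the study to show signals on nocturia and looks to the nocturia quality-of-life questionnaire to quantify the impact on subjects' lives. For an underpowered exploratory endpoint, an estimate with its interval is the most useful result. As planned, ICIQ-NQoL has none.

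The selection is also unexplained. Awakenings come from the same diary and use the same weekly averaging as the VAS scores, but only the VAS scores are modelled. A treatment-satisfaction rating gets a paired interval and the nocturia quality-of-life score does not.

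**Working it through.** **1. Coverage of the nocturia endpoints in Protocol Table 3**

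| Endpoint | SAP section | Within-subject comparison | CI for treatment difference |
|---|---|---|---|
| Number of nocturnal voids | 6.3.2.5.2 | MMRM | yes |
| Time to first nocturnal void | 6.3.2.2 | sign test | none stated |
| Volume of first nocturnal void | 6.3.2.3 | no | no |
| Total night volume | 6.3.2.4.2 | no | no |
| Number of daytime voids | 6.3.2.5.2 | no | no |
| Total daytime volume | 6.3.2.4.2 | no | no |
| ICIQ-NQoL | 6.3.3.2.2 | no | no |
| LUTS sub-scores | 6.3.3.1.2 | no | no |

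Six of eight lack a within-subject comparison and seven of eight lack a CI. Awakenings are outside this count because they belong to the primary objective.

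**2. The plan's own sTST figures**

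The per-treatment SDs of 42.5 min (placebo) and 50.5 min (daridorexant) are in the Protocol synopsis; the correlation of 0.58 is in Protocol 9.4.

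SD of the difference = sqrt(42.5² + 50.5² − 2 × 0.58 × 42.5 × 50.5) = sqrt(4356.5 − 2489.65) = 43.2 min. The stated 44 is slightly conservative.

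For the assumed mean difference, Protocol 9.4 states: "26 min and an associated SD of 44 min, a total sample size of 50 subjects, in this cross-over setting, provides at least 90% power". The exact paired t-test (df 49) gives 98.4%, and 88.3% for the 20 min fallback. Both agree with the stated lower bounds of 90% and 80%.

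**3. What pairing is worth on those figures (N = 50)**

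- Paired: SE = 44/sqrt(50) = 6.22 min; 95% half-width 12.5 min.
- As if independent: SE = sqrt((42.5² + 50.5²)/50) = 9.33 min; 95% half-width 18.5 min.
- Ratio 9.33/6.22 = 1.50.

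The two column SDs do not settle which SE applies. With the same SDs, a correlation of 0.3 gives an SD of the difference of sqrt(4356.5 − 1287.75) = 55.4 min, and 0.7 gives sqrt(4356.5 − 3004.75) = 36.8 min.

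**4. Illustration for the descriptive-only scales**

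The documents give no SD or correlation for these scales. With equal SDs, paired SE / independent SE = sqrt(1 − ρ). Half-widths are in units of the per-treatment SD; treating the columns as independent gives 0.40.

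| Assumed ρ | SE ratio | Reduction | Paired 95% half-width |
|---|---|---|---|
| 0.3 | 0.837 | 16% | 0.34 |
| 0.5 | 0.707 | 29% | 0.28 |
| 0.58 (sTST value) | 0.648 | 35% | 0.26 |
| 0.7 | 0.548 | 45% | 0.22 |

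**5. Period effect in the column difference**

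SAP 2: "Approximately 50 subjects will be randomized in a 1:1 ratio to one of two treatment sequences". If an additive effect π acts in Period II, the daridorexant column carries π × n(placebo first)/N and the placebo column π × n(daridorexant first)/N. The difference keeps π × [n(placebo first) − n(daridorexant first)]/N. That is 0 at 25/25 and 2/50 = 4% of π at 26/24. SAP 6.1.4 expects under 3% dropout, so the residue stays small.

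**The case against.** The strongest reply is that this is a permitted choice. No secondary endpoints are defined, only sTST is claimed to be adequately powered, and the protocol defers the remaining analyses to the SAP. The one nocturia endpoint with power scenarios (Protocol 9.4.1) does receive the cross-over model, on three derivations. That stands: the SAP breaks no commitment. It does not explain why the variables of a stated objective go without an interval when other exploratory scales get one.

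A reader might infer more than the documents support:

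- *No nocturia endpoint is compared within subjects.* Two are: nocturnal voids and time to first void.
- *No treatment difference can be obtained.* With complete data the difference in column means equals the mean within-subject difference. SAP 6 also lists individual efficacy data on the FAS, so someone holding the listings could rebuild the pairs. The reported tables lack the SE and CI.
- *Period effects bias the columns.* Under 1:1 sequences and low dropout an additive effect almost cancels. Balance within each sex is less assured, since randomization is unstratified (Protocol 6.1.4).
- *The gain is known to be 35%.* The 0.58 is an sTST correlation from another study in subjects aged 65 and over. It is borrowed here.

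A further objection concerns multiplicity and stands in part. The full fix adds about 26 intervals: awakenings 4, first-void volume 2, night volume 6 (three derivations, two weeks), night-plus-morning, morning and daytime volume 6, daytime voids 2, LUTS 5, NQoL 1. If all were null and independent, which they are not, the chance that at least one excludes zero is 1 − 0.95^26 = 74%. This calls for clear labelling and for putting ICIQ-NQoL first. It is no reason to omit estimates.

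**Conclusion.** The point holds as a gap in estimation. Six of eight nocturia endpoints, and the number of awakenings under the primary objective, will be reported without the paired SE or CI that the design makes available. The size can be given only in relative terms: a paired SE 16% to 45% below the independent-columns value for assumed correlations of 0.3 to 0.7, with equal SDs and about 50 near-complete subjects.

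A reader might take this as a flaw in the confirmatory analysis. It is not. The only hypothesis covered by "The null hypothesis will be tested at a 2-sided 0.05 significance level" is the sTST comparison, which has its own within-subject model. The change is worth making because the data and most of the model already exist and the endpoints serve a stated objective.

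**What to change.** Before unblinding, add the LS mean difference (daridorexant minus placebo) with 95% CI to these SAP sections, in this order of priority:

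1. 6.3.3.2.2, ICIQ-NQoL.
2. 6.3.3.1.2, LUTS sub-scores, fitted within each sex.
3. 6.3.2.3, 6.3.2.4.2 and 6.3.2.5.2: first-void volume, total volumes and daytime voids.
4. 6.3.1.3, number of awakenings.

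Where an endpoint has more than one week per period, use the cross-over MMRM of 6.1.3 or 6.3.2.5.2. ICIQ-NQoL and LUTS have one value per period, so the week terms and the unstructured week covariance in SAP 13.2 drop out. Specify a reduced mixed model for them with treatment, period, baseline and a random subject effect.

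Label the results as exploratory estimation without multiplicity control, keep the descriptive tables, and record the addition in SAP 11.4.

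The cost is SAP text, one short additional model specification and extra table rows. No new data are needed. The downsides are more unadjusted intervals, and wide ones for the sex-specific LUTS scores because about 50 subjects are divided by sex.

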# 6.3.3.3 EQ-5D-3L

The EQ-5D-3L is an instrument that assesses quality of life, irrespective of the disease. The 5 dimensions include mobility, self-care, usual activities, pain/discomfort, and anxiety/depression. 'None', 'some', and 'extreme' are the 3 modalities for each dimension. Depending on the box checked by the subject, a number is assigned to each dimension resulting into a 5-digit number combination (e.g., a completely healthy subject would have a score of 11111). It will be completed by the subjects at Visit 1, Visit 3, Visit 4, Visit 7, and Visit 8.

#### 6.3.3.3.1 Variable

As the study is mainly conducted in the Unites States, the derivation of the scores for EQ-5D-3L follows the publication by Shaw et al. [Shaw 2005]

Each of the 5-digit number combinations is assigned a score, e.g., for combination 11111 a score of 1.000 is assigned, while for combination 12332 a score of 0.302 is assigned. The assignments of all scores are summarized in Appendix 13.4.

### 6.3.3.3.2 Analysis

The change from baseline to Week 2 and Week 4 for the overall EQ-5D-3L score will be summarized by treatment. Observed values will also be summarized.

## 6.3.3.4 PGA-S and PGI-C endpoints

## 6.3.3.4.1 PGA-S endpoints

The PGA-S (daytime symptoms) is indicative of the overall severity of daytime symptoms (e.g., sleepiness) and impact (e.g., effort to perform daily activities) that the subject may have experienced due to their *insomnia* over the 7 days preceding the PGA-S. The PGA-S (daytime symptoms) is a 1-item, 6-point scale that ranges from 'None' to 'Very severe'. It will be completed by the subjects on the eDiary at Visit 1 and weekly during both treatment periods.

The PGA-S (daily life) is indicative of the overall impact on daily life (e.g., effort to perform daily activities) that the subject may have experienced due to their *insomnia and nocturia* over the 4 weeks preceding the PGA-S. The PGA-S (daily life) is a 1-item, 5-point scale that ranges from 'Not at all' to 'Extremely'. It will be completed by the subjects on the eDiary at Visit 1, Visit 4, and Visit 8.

Confidential

Statistical Analysis Plan for Clinical Study Report Version 2 Doc No D-24.149

#### 6.3.3.4.2 *Variable*

Page 31/50

The PGA-S (daytime symptoms) scales ranges from 1–6, the PGA-S (daily life) ranges from 1–5. Changes from baseline will be calculated.

Time windows will be assigned for both PGA-S assessments due to missing visit labels in the eDiary database. Data were supposed to be collected on Day 8 (Week 1), Day 15 (Week 2), Day 22 (Week 3) and Day 29 (Week 4) after treatment start date for PGA-S (daytime symptoms) and on Day 29 (Week 4) after treatment start date for PGA-S (daily life) in each treatment period.

PGA-S (daytime symptoms) data for Week 1–Week 3 were collected based on a 7-day schedule in the eDiary. A time window of  $\pm$  2 days will be assigned to those weeks to select the data (Days 6–10 for Week 1, Days 13–17 for Week 2, and Days 20–24 for Week 3). As the Week 4 data was collected during the hospital visit, the variability of the collection dates is higher. Therefore, a time window of -4 to +7 days will apply for Week 4 (Days 25–36; no overlap with Week 3 data). If two data points were collected within the same time window, the collection date closest to the pre-defined days will be used (Day 8 for Week 1, Day 15 for Week 2, Day 22 for Week 3, and Day 29 for Week 4). Data will be assigned independent of visit labels.

For PGA-S (daily life) a time window of  $\pm$  7 days will apply for Week 4. If 2 data points were collected within the same time window, the collection date closest to the pre-defined day will be used (as defined above).

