Treatment period preference										Х	X ³	
Narrative		Х			Х					Х	X ³	
Study treatment dispensing/return			Х		Х			Х		Х	X ³	
Study drug intake			•		►			-		► ►		
Treatment acco	ountability				Х					Х	X ³	
SAEs/AEs ¹		•										

¹ All AEs and SAEs that occur after signing the ICF and up to 5–10 days after study treatment discontinuation must be reported [see also Section 8.1 and 8.2].

² Must be done before randomizing the subject.

³ Only applicable for subjects who prematurely discontinued study treatment. All subjects withdrawn from study treatment will be encouraged to follow planned study procedures (e.g., visits, diary and questionnaire completion until planned EOS visit) provided that the subject's consent for this limited participation in the study has not been withdrawn.

⁴Will be completed by phone call.

⁵PGA-S and PGI-C (daytime symptoms and nighttime symptoms questionnaires) will be completed at home once a week between Visit 2 and Visit 8. The patient global scales are completed on the same days.

⁶The hand-held device is handed out to the subject and completed at home daily from Visit 1 to Visit 8.

Daridorexant (ACT-541468)	
Insomnia and comorbid nocturia	
Protocol ID-078A401	Confidential
Version 3	
4 September 2023, page 30/122	

⁷The voiding diary must be completed by the subjects for 3 consecutive days and nights after the Visit 1, Visit 2 and Visit 6 as well as for 3 consecutive days and nights immediately preceding Visit 4 and Visit 8, respectively [see Table 2]. The investigator should plan the completion of the diary according to the visit schedule.

⁸The IDSIQ will be administered from Visit 1 to Visit 8 and completed daily.

⁹The ICIQ-MLUTS will only be given to male subjects, while females will receive the ICIQ-FLUTS.

*The site will contact the subject to remind him/her to complete the voiding diary for 3 consecutive days preceding the EOTP visit.

** The subject will be asked to return for a PEOT visit within 5 days of last intake of study treatment and thereafter to attend the following visits up to the respective EOTP visit.

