4.3 Study design rationale

The randomized, placebo-controlled, 2-way cross-over study setting is considered adequate to prevent and account for bias in the endpoints that are assessed, as every subject will act as their own control, resulting in reduced variability and, therefore, also in a smaller sample size. Furthermore, a cross-over design is adequate to assess chronic conditions like insomnia and nocturia as it is not expected that the disease status changes over the duration of study. To avoid the risk of carry-over, a washout period of 14–21 days is implemented between the two treatment periods to allow variables to return to baseline conditions. This is considered adequate given the half-life of 8 h of daridorexant.

This study is a post-approval investigation to study efficacy and safety in subjects with insomnia and comorbid nocturia. In line with the EMA guideline on medicinal products for the treatment of insomnia [EMA 2011], the FDA guideline for the clinical evaluation of hypnotic drugs [FDA 1977] as well as the entire clinical developmental program of daridorexant, this study includes a placebo group to allow proper characterization of the efficacy and safety results of daridorexant. The use of a placebo group for a period of 1 month in this population is considered medically acceptable.

Data from the Phase 2 and Phase 3 studies support the duration of the treatment period of 29 days \pm 2 days to assess subjective changes in day- and nighttime variables in subjects with insomnia. No placebo run-out is included in the trial, as the Phase 3 studies did not indicate any withdrawal symptoms and/or rebound effect, which is anticipated to be similar in this population. Potential AEs related to the cessation of the study drug will be assessed during the 5–10 day follow-up period.

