# 6.3.3.4.4 PGI-C endpoints

The PGI-C (daytime symptoms) is indicative of the change in overall severity of daytime symptoms (e.g., sleepiness) and impact (e.g., effort to perform daily activities) that the subject may have experienced due to their *insomnia* over the 7 days preceding the PGI-C (daytime symptoms) compared to the week before he/she started treatment. The PGI-C (daytime symptoms) is a 1-item, 7-point scale that ranges from 'Very much better' to 'Very much worse'. It will be completed weekly by the subjects on the eDiary during both treatment periods.

The PGI-C (nighttime symptoms) is indicative of the change in the subject's insomnia symptoms at night (e.g., trouble falling asleep, total time asleep, time to fall back asleep or number of times they wake up) over the 7 nights preceding the PGI-C (nighttime symptoms) compared to the week before the subject started treatment. The PGI-C (nighttime symptoms) is a 1-item, 7-point scale that ranges from 'Very much better' to

'Very much worse'. It will be completed weekly by the subjects on the eDiary during both treatment periods.

The PGI-C (daily life) is indicative of the change in overall severity of daily life symptoms that the subject may have experienced due to their *insomnia and nocturia* over a period of 4 weeks. The PGI-C (daily life) is a 1-item, 5-point scale that ranges from 'Very much better' to 'Very much worse'. It will be completed by the subjects on the eDiary at Visit 4 and Visit 8.

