#### 6.3.3.4.5 *Variable*

The PGI-C (daytime symptoms) scale ranges from 1–7, the PGI-C (nighttime symptoms) ranges from 1–7, and the PGI-C (daily life) ranges from 1–5.

The same time window approach will be used for PGI-C (daytime symptoms) data as described in Section 6.3.3.4.2.

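### The Week 4 window for the daytime-symptom PGA-S and PGI-C (Days 25–36) is not tied to the last dose or the EOTP visit, so a late rating can describe mostly washout

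*SAP*

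**What the plan says.** SAP 6.3.3.4.2 assigns PGA-S (daytime symptoms) ratings to weeks by calendar day because visit labels are missing from the eDiary database. Weeks 1 to 3 have windows of ± 2 days. Week 4 is wider: "a time window of -4 to +7 days will apply for Week 4 (Days 25–36; no overlap with Week 3 data". The SAP's reason is that the Week 4 rating was taken at the hospital visit, whose date varies more. If two ratings fall in one window, the one closest to the target day (Day 29 for Week 4) is used. Assignment ignores visit labels.

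SAP 6.3.3.4.5 adds: "The same time window approach will be used for PGI-C (daytime symptoms) data as described in Section 6.3.3.4.2". It gives no window for the PGI-C (nighttime symptoms).

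The recall periods are short. The PGA-S (daytime symptoms) asks about symptoms "over the 7 days preceding the PGA-S" (SAP 6.3.3.4.1), and the PGI-C (daytime symptoms) asks about change "over the 7 days preceding the PGI-C (daytime symptoms) compared to the week before he/she started treatment" (SAP 6.3.3.4.4).

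On the end of dosing, SAP section 2 says that a treatment period "ends on the day after the last dose of study treatment (Day 29" in the nominal schedule. Protocol Table 1 allows the EOTP visit on Day 29 ± 2, and Protocol 4.1.1 places EOTP on the morning after the last evening dose. A washout of 14–21 days follows Period I.

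On collection, Protocol Table 1 footnote 5 says that the scales "will be completed at home once a week between Visit 2 and Visit 8". Protocol 3.2.4 to 3.2.6 restrict the weekly ratings to the two treatment periods.

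**The concern.** A scale with a 7-day recall measures treatment only if most of those 7 days were treated. The window runs to Day 36, a week after the nominal end of the period, and no rule checks when the subject last took study drug. The protocol justifies the washout length with the remark "This is considered adequate given the half-life of 8 h of daridorexant", so days after the last dose are soon off drug.

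Off-treatment ratings would then enter the Week 4 summaries as if they described treatment. For daridorexant this would tend to blur any difference from placebo. The plan is stricter for sTST: Protocol 9.2.2.2 excludes data after the EOTP visit, and SAP 6.1.1 stops the weekly averages at Day 29.

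Footnote 5 suggests one possible route. Read literally, its interval includes the washout, and a rating one week after Day 29 falls on Day 36, the last admitted day.

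**Working it through.** **Inputs**
- Week 4 target Day 29, window −4 to +7; Week 3 target Day 22, window ± 2 (SAP 6.3.3.4.2).
- Recall of 7 days for both daytime scales (SAP 6.3.3.4.1 and 6.3.3.4.4).
- EOTP visit on Day 29 ± 2 (Protocol Table 1), on the morning after the last dose (Protocol 4.1.1).

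**1. Reproduce the stated window.** 29 − 4 = 25 and 29 + 7 = 36. Week 3 is 22 ± 2, or Days 20–24. The SAP's figures are correct, including the absence of overlap.

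**2. Range of on-schedule last doses.** EOTP falls on Days 27 to 31, so the last dose falls on the evening of Days 26 to 30 (nominally Day 28).

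**3. Treated days in the recall.** Let L be the day of the last dose and R the day of the rating. A day counts as treated if it follows a dosed night, that is, if it is no later than L + 1. If the recall covers days R − 7 to R − 1, the count is L + 9 − R. If the rating day itself is counted (R − 6 to R), it is L + 8 − R. Both are limited to the range 0 to 7.

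Treated days of 7, with the second convention in brackets:

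| Last dose | Rating Day 31 | Rating Day 33 | Rating Day 36 |
|---|---|---|---|
| Day 26 | 4 (3) | 2 (1) | 0 (0) |
| Day 27 | 5 (4) | 3 (2) | 0 (0) |
| Day 28 | 6 (5) | 4 (3) | 1 (0) |
| Day 29 | 7 (6) | 5 (4) | 2 (1) |
| Day 30 | 7 (7) | 6 (5) | 3 (2) |
| Day 35 (late EOTP, dosing continued) | 7 (7) | 7 (7) | 7 (7) |

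For every on-schedule last dose, a Day 36 rating has at most 3 treated days of 7. With the last dose on Day 28, the recall becomes mostly untreated from Day 34 (28 + 9 − 34 = 3), or from Day 33 on the second convention (28 + 8 − 33 = 3).

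**4. When a Day 36 rating is used.** It lies 7 days from the target and every other day in the window lies closer. It is therefore selected only if there is no rating on Days 25–35.

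**5. A limit of 4 days after the last dose.** With R = L + 4 the counts are 9 − 4 = 5 and 8 − 4 = 4 of 7. With R = L + 5 they are 4 and 3. Four days is thus the latest point with a treated majority on both conventions.

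**6. Daily-life scale for comparison.** The PGA-S (daily life) recalls 4 weeks. With the last dose on Day 28, a Day 36 rating covers Days 8–35, of which Days 8–29 are treated: 22 of 28. It is not affected in the same way.

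**The case against.** The strongest counter-argument is that the SAP explains the wide window. Only Weeks 1–3 came from the 7-day eDiary schedule. Week 4 was rated at the visit, so a late rating should mean a late EOTP visit. EOTP is by definition the morning after the last dose, Protocol Appendix 1 lets visits slip while study treatment lasts, and SAP 6.1.1 foresees treatment beyond 4 weeks. A reader might infer that any Day 36 rating measures washout, and the documents do not support that: with dosing to Day 35, all 7 recalled days are treated. This part of the objection stands. It does not remove the gap, because the SAP requires neither that a late rating come from the EOTP visit nor that it follow a recent dose.

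The footnote 5 route is also uncertain. Protocol 3.2.4 to 3.2.6 and SAP 6.3.3.4.1 and 6.3.3.4.4 confine weekly ratings to the treatment periods, so washout collection is the weaker reading. A reader might further infer that only Period I is exposed, so that dilution depends on sequence. That holds only on the footnote reading; a visit held some days after the last dose could occur at Visit 4 or Visit 8.

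The comparison with sTST is fair only in part. Daily diary entries can be cut at Day 29, whereas a single visit-based rating cannot, so some tolerance is reasonable.

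Finally, a limit of 4 days is a judgement, and it would drop a completer with 3 treated days while keeping an early stopper with none. The difference is defensible. Stopping early is an intercurrent event, and Protocol 9.2 uses data regardless of such events; planned washout after a completed period is not one.

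**Conclusion.** The concern holds in a limited form. As written, the rule can count a rating as Week 4 when at most 0 to 3 of its 7 recalled days were treated, for a subject whose last dose fell on Days 26–30 and whose only rating in the window is on Day 36. This rests on the stated recall periods, on the permitted visit window, and on treating days after the morning following the last dose as off treatment.

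The size of any effect on the treatment summaries cannot be stated. The documents do not say how many Week 4 ratings fall after Day 31 or how many subjects lack an earlier one, so a percentage dilution would be a guess. The scales are other efficacy endpoints, summarized descriptively without a test (SAP 6.3.3.4.3 and 6.3.3.4.6), so the primary result is untouched. This is a cheap improvement to the SAP and does not threaten the trial's conclusions.

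**What to change.** In SAP 6.3.3.4.2 and 6.3.3.4.5, keep Days 25–36 and add two conditions for Week 4:
- The rating is dated on or before the EOTP visit of that treatment period.
- For subjects recorded as having completed that period's treatment as planned, the rating is close enough to the treatment end date that most of the recall is treated, for example no more than 4 days after the last dose.

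Otherwise set Week 4 to missing. Subjects with extended dosing stay in, because the limit follows their actual last dose. Subjects who stopped early keep their ratings up to EOTP under treatment policy.

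Apply the same window and conditions to the PGI-C (nighttime symptoms), which recalls 7 nights on the same weekly schedule. Reconcile Protocol Table 1 footnote 5 with Protocol 3.2.4 to 3.2.6, so that it is clear whether ratings were collected during washout.

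The cost is a sentence or two in the SAP and one programming condition on dates already available (treatment end date in SAP 10.1, completion status in SAP 5.1.2). The downside is that a few Week 4 ratings become missing. Reporting how many would show whether the issue mattered.
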